4.1 Primary endpoint

The primary endpoint - **Cerebrovascular Ischemia**, major **Hemorrhagic events** or **Death (CIHD)** - is a composite endpoint. It is defined as the occurrence of at least one of the following events during the treatment period:

1. Cerebral ischemic events (clinical) or surrogate findings for cerebral ischemia:
 - (a) Any ischemic stroke, defined as: new symptomatic neurologic deterioration lasting at least 24 hours that was not attributable to a non-ischemic cause, or a new symptomatic neurologic deterioration that was not attributable to a non-ischemic cause and was accompanied by neuroimaging evidence of a new brain infarction. ([Amarenco et al. \(2018\)](#)). This includes Transient Ischemic Attack (TIA) with Diffusion Weighted Imaging (DWI) lesion. Ischemic stroke also includes retinal infarction defined according to ([Hayreh & Zimmerman \(2005\)](#))
 - (b) New acute ischemic lesions on DWI MRI since baseline are defined as: (1) those with an unequivocal lack of continuity between new and existing (on baseline imaging) lesions on the same slice as well as on adjacent slices – irrespective of vascular territories and lesion pattern, ([Gensicke et al. \(2015\)](#)) and (2) “acute” being defined as a hyperintense signal alteration on DWI with a corresponding hypointense or isointense signal on ADC (Apparent Diffusion Coefficient) maps ([Gensicke et al. \(2015\)](#)).
2. Hemorrhages (clinical) or surrogate findings:
 - (a) any major extracranial hemorrhage: any clinically apparent extracranial bleeding requiring any kind of intervention [including hospitalization or prolongation of hospitalization] or leading to death.
 - (b) any symptomatic intracranial hemorrhage defined as: any documented intracranial hemorrhage - i.e. an acute extravasation of blood into the brain parenchyma ([Amarenco et al. \(2018\)](#)) - that was temporally related to any deterioration in the patient’s clinical condition.
 - (c) any new, asymptomatic micro- or macrobleeds (visible on follow-up brain T2*-MRI or Susceptibility weighted imaging (SWI), which were absent on the baseline MR-scan) defined as: (1) those with an unequivocal lack of continuity between new and existing (on baseline imaging) lesions on the same slice as well as on adjacent slices – irrespective of vascular territories and lesion pattern, ([Gensicke et al. \(2015\)](#)) and lesions being defined as hypointense brain lesions with clear margins on T2*-MRI or SWI.
3. Death of any course: In an adjudication procedure, causes of death will be distinguished as cardio/cerebrovascular (i.e.: fatal acute coronary syndrome, fatal stroke, fatal intracranial hemorrhage, fatal pulmonary embolism, sudden death, and unobserved or unexpected death) ([Amarenco et al. \(2018\)](#)) vs all other causes.

If MR-sequences required to detect micro- or macrobleeds (i.e. T2* or SWI-sequence) were not performed at baseline, any micro- or macrobleeds seen in the follow-up

MRI will be considered as new³. The number of patients for whom the baseline MR-sequences required to detect micro- or macrobleeds were not performed and their patient characteristics at baseline will be presented.

4.2 Hypothesis

We will test the following null hypothesis:

$$H_0 : \pi_{\text{anti-platelet treatment}} \geq \pi_{\text{anti-coagulant treatment}} + \delta \quad (1)$$

where δ is the non-inferiority margin. The alternative hypothesis is:

$$H_1 : \pi_{\text{anti-platelet treatment}} < \pi_{\text{anti-coagulant treatment}} + \delta \quad (2)$$

where π is the probability of a CIHD under the indicated treatment.

The non-inferiority margin is set to $\delta = 0.12$ (12 % absolute risk difference).

4.3 Model and method of analysis

The difference in CIHD rate $\pi_{\text{anti-coagulant treatment}} - \pi_{\text{anti-platelet treatment}}$ will be compared with the non-inferiority margin using a two-sided 95 % confidence interval. We will use Wilson's method to calculate CI (continuity-corrected modification of the Wilson's score method [Newcombe, 1998](#)). The primary analysis will be performed on the PP. Section 5.2 describes the handling of missing values.

4.4 Presentation of results

We provide the point estimate together with its 95 % confidence interval. This approach will also allow us to assess superiority of either treatment.

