Biomarkers and antithrombotic treatment in cervical artery dissection
The TREAT-CAD trial

ClinicalTrials.gov Identifier: NCT 02046460

Statistical analysis plan – dated Dec. 18th 2019

[name]. [name]
Universitätsspital Basel
Neurologie
[name]
[name]

Basel, December 18, 2019

Methods & Statistics

Study Title	Biomarkers and antithrombotic treatment in cervical artery dissection
Internal DKF ID	[name]
Document Status	Confirmed Final Report

This statistical report and analysis plan will be finalized before database closure and will be under version control at the Clinical Trial Unit, University Hospital Basel.

1 Background

Antithrombotic treatment in cervical artery dissection (CAD) is still a matter of debate. Most physicians prescribe anticoagulants for stroke prevention in CAD-patients although this approach is not evidence-based.

This randomized controlled, open labeled multicenter non-inferiority trial with blinded assessment of outcome events compares anticoagulant treatment to antiplatelet treatment.

2 Analysis data sets

The **full analysis set (FAS)** consists of all patients that were randomized. According to the intention-to-treat principle, each patient will be analyzed according to the treatment she/he was randomly allocated to. Patients who withdrew their consent during the course of the study will be analyzed in the FAS including only their baseline data.

The **per protocol set (PP)** consists of patients in the FAS set without any of the following major protocol deviation:

- no dissection: diagnostic criteria for CAD not met in central MR reading
- violation of an inclusion criterion or having an exclusion criterion (for pregnancy, only a positive pregnancy test will be considered as a major protocol deviation)¹
- switching between treatment groups (cross-over) or discontinuation of the allocated treatment before follow-up visit 2 for any reason other than as a reaction to a primary outcome-event or an SAE
- MRI at follow-up visit 1 earlier or later than 14 +/- 10 days
- follow-up visit 2 prior to 60 days after randomization ²

The following deviations will be considered as minor protocol deviations:

- result of pregnancy test too late but negative (ie. confirmed absence of pregnancy after inclusion and randomization)
- randomization or start of treatment allocated not within 72h after initial MRI scan

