- changes in treatments within the allocated treatment arm (eg. dosage of ASA 100mg rather than 300 mg) prior to follow-up visit 2

Patients with only minor protocol deviations will still be part of the PP.

Each patient will be analyzed according to the treatment she/he received until follow-up visit 2.

3 Demographic and baseline characteristics

Demographics and relevant baseline variables will be summarized for the PP and the FAS set. All summaries will be broken down by the treatment patients received.

Categorical data will be presented as frequencies and percentages. For continuous variables, the total number of measurements as well as the mean and the standard deviation will be presented. For skewed data the median and the lower and upper quartile will be shown.

4 Primary objective

The primary objective is to demonstrate the non-inferiority of anti-platelet treatment to anti-coagulant treatment in preventing further cerebrovascular ischemic events in patients with cervical artery dissection (CAD).

¹The protocol does not distinguish between “confirmed absence of pregnancy” and “assumed but unconfirmed absence of pregnancy”. We only consider the latter as a major protocol deviation since patients with a late but negative pregnancy test are still part of the intended study population.

²In the protocol the window for visit 2 was 90 +/-30 days.

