4.5 Supportive analyses and sensitivity analyses

The following supportive and sensitivity analyses will be conducted to support the main analysis described above (Section 4.3). The rationale for each sensitivity analysis is indicated in bold. All sensitivity analyses except for the sensitivity analysis nr 2 will be performed on the PP. Missing values will be handled as described in section 5.2 if not defined otherwise.

1. **Missing values:** In case of missing values for the primary endpoint, the main analysis will be repeated performing the following imputations

³In the protocol, this was planned as sensitivity analysis. However, given the rather young patient population, we do not expect preexisting micro- or macrobleeds. Therefore the probability of falsely labeling an existing microbleed as new due to missing baseline T2* - or SWI MRI was considered to be small and the aim to preserve the randomization was of overriding importance. Therefore the two analyses were switched.

- (a) Missing values in the primary endpoint will be imputed as CIHD events (assuming the worst for patients without follow-up).
 - (b) Missing values in the primary endpoint will be imputed as no CIHD events (assuming the best for patients without follow-up).
2. **Choice of analysis population (PP vs. FAS):** The analysis will be repeated on the FAS and compared to the main analysis. According to the intention-to-treat principle, each patient will be analyzed according to the treatment she/he was randomly allocated to. In case of missing values for the primary endpoint, the following imputations will be performed:
 - (a) Missing values in the primary endpoint will be imputed as CIHD events (assuming the worst for patients without follow-up).
 - (b) Missing values in the primary endpoint will be imputed as no CIHD events (assuming the best for patients without follow-up).
 - (c) Patients with missing values in the primary endpoint will be excluded from the analysis. Inverse probability of censoring weights will be used as described for the main analysis in section 5.2.
3. **Incomplete information about micro- or macrobleeds at baseline:** The main analysis will be repeated excluding patients without baseline information with regards to micro- or macrobleeds.

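### Section 4.4 reads superiority of either treatment from the per-protocol interval; it should rest on the planned full-analysis-set comparison by allocated arm

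*SAP*

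**What the plan says.** SAP section 4.2 states hypotheses for non-inferiority only, with a margin of 12 percentage points. Section 4.3 compares the risk difference with that margin through a two-sided 95% continuity-corrected Newcombe interval, and fixes the set: "The primary analysis will be performed on the PP". Section 4.4 then says of the same estimate and interval: "This approach will also allow us to assess superiority of either treatment".

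Section 2 defines the PP. Among its exclusions are cross-over or discontinuation before follow-up visit 2 "for any reason other than as a reaction to a primary outcome-event or an SAE", a first follow-up MRI outside its window, and an early visit 2. On grouping it says: "Each patient will be analyzed according to the treatment she/he received until follow-up visit 2". Section 1 describes an "open labeled multicenter non-inferiority trial with blinded assessment of outcome events".

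The comparison by allocated arm appears in section 4.5 as sensitivity analysis 2: "The analysis will be repeated on the FAS and compared to the main analysis". It has three versions for missing endpoints: (a) all counted as events, (b) all counted as non-events, and (c) excluded, with inverse probability of censoring weights. The other sensitivity analyses stay on the PP.

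**The concern.** Making the PP primary for non-inferiority is not in dispute. The difficulty is that section 4.4 carries the same set over to superiority, where the usual reason for preferring the PP does not apply.

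Whether a patient who stops treatment remains in the PP depends partly on the outcome. Someone who stops because of a primary event stays in and counts as an event; someone who stops without an event, for another reason, is removed along with an event-free result. If stopping differs between arms, as it can when treatment is known, the arm with more stopping loses more event-free patients and its PP event rate rises. Two equally good treatments can then look different, and section 4.4 would allow that difference to be read as superiority.

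The SAP recognises this type of bias: the footnote to sensitivity analysis 4 gives it as the reason for adding a weighted analysis. It does not say which set decides superiority if PP and FAS disagree.

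**Working it through.** **No figure to reproduce.** The SAP gives no sample size, event rate or stopping rate. All inputs below except the interval method and the 95% level are assumptions.

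**Bias formula.** Let p be the true risk, s the proportion stopping for reasons other than an SAE, and q the share of stoppers' events that come before the stop and are taken to have prompted it. Then

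PP rate = p(1−s+sq) / [p(1−s+sq) + (1−p)(1−s)].

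Take p = 0.17 in both arms (no treatment effect) and s = 5% in one arm.

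With q = 1:
- s = 5%: 0.17/(0.17 + 0.83×0.95) = 0.17/0.9585 = 17.7%
- s = 15%: 0.17/(0.17 + 0.83×0.85) = 0.17/0.8755 = 19.4%, a spurious difference of 1.7 points
- s = 25%: 0.17/(0.17 + 0.83×0.75) = 0.17/0.7925 = 21.5%, a difference of 3.7 points

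With q = 0.5:
- s = 5%: 0.16575/0.95425 = 17.4%
- s = 15%: 0.15725/0.86275 = 18.2%, a difference of 0.9 points

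With q = 0 the formula returns p, so there is no bias.

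**False superiority, stopping unrelated to risk.** Each scenario used 400,000 simulated trials with the SAP's interval and complete endpoints. Ranges run from q = 50% to q = 100%. Repeat runs differ by about 0.1 point.

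| Per arm | Stopping | Bias (points) | PP, favouring the arm with less stopping (nominal 2.5%) | PP, both directions (nominal 5%) |
|---|---|---|---|---|
| 95 | 5% vs 10% | 0.4-0.8 | 2.1-2.5% | 3.5-3.7% |
| 95 | 5% vs 15% | 0.9-1.7 | 2.4-3.5% | 3.6-4.3% |
| 95 | 5% vs 25% | 1.9-3.7 | 3.7-6.7% | 4.4-7.0% |
| 200 | 5% vs 15% | 0.9-1.7 | 3.3-5.0% | 4.4-5.7% |
| 200 | 5% vs 25% | 1.9-3.7 | 5.6-12.0% | 6.2-12.1% |

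The FAS gives 1.7% (3.3% in both directions) at 95 per arm and 2.0% (3.9%) at 200.

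**Stopping related to risk.** Let 20% of patients have a risk of 45% and the rest 10% (0.2×0.45 + 0.8×0.10 = 0.17). The high-risk group stops 2.7 times as often, with the same overall stopping rates. At 95 per arm:
- 5% vs 15%: 2.0-3.2%, bias 0.4-1.5 points
- 5% vs 25%: 2.4-6.0%, bias 0.8-3.3 points
- If no event precedes stopping (q = 0), the bias reverses, to 0.9 and 2.0 points the other way.

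**Does sensitivity analysis 4 repair this?** Suppose its weights were estimated by arm and its covariates captured risk fully. With s equal across the two risk groups and q = 1, apply the formula within each group and reweight to the FAS mix:
- s = 5%: 0.2×0.4627 + 0.8×0.1047 = 17.6%
- s = 15%: 0.2×0.4905 + 0.8×0.1156 = 19.1%
- s = 25%: 0.2×0.5217 + 0.8×0.1290 = 20.8%

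The bias falls only from 1.7 to 1.4 points and from 3.7 to 3.1. Baseline weights cannot undo retention that depends on the outcome itself.

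**Other inputs.** Take 100 per arm and 20% risk, with all events kept and 20% vs 5% of event-free patients excluded. The PP rates are 0.20/0.84 = 23.8% and 0.20/0.96 = 20.8%, a difference of 3.0 points. False superiority is 5.4%, against 1.8% on the FAS. With 10% excluded in both arms, the PP shows no inflation.

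**The case against.** The strongest reply is that the SAP plans no superiority test. Its hypotheses concern non-inferiority only, the sentence in 4.4 is a remark about presentation, and the FAS result will be reported beside the PP result, so a reader would see any disagreement. This stands, and it keeps the weight low to moderate. It does not supply the missing rule on which result decides.

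The size also depends on assumptions, and several soften it. At 95 per arm, 5% vs 10% stopping stays at or below nominal, and the two-direction rate exceeds 5% only at the upper end of 5% vs 25%. The model treats every event before a stop as its cause; a patient who has an event and later stops for an unrelated reason would be excluded, which lowers q. At q = 25%, 5% vs 25% gives 2.6% and a bias of 1.0 point. Stoppers retained after a non-primary SAE are not modelled. If 25% is taken as all stopping and 30% of event-free stoppers stay in for that reason, the range becomes 2.3-4.5%. All of this limits the size; none of it makes the PP a randomised comparison.

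Finally, the FAS figures assume complete endpoints. Patients who withdraw consent contribute baseline data only, and version 2(c) weights on the same four baseline variables as sensitivity analysis 4. That is a real limitation of the remedy and the reason to keep 2(a) and 2(b) as checks.

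**Conclusion.** The concern holds. As written, superiority of either treatment would be read from the PP interval, and nothing in the SAP assigns it to another set. The consequence is a possible false superiority finding, not a demonstrated one. Its size and direction cannot be derived from the SAP. Under the assumed inputs, mild imbalance in stopping matters little, strong imbalance can raise the one-direction error well above 2.5%, and risk-selective stopping can offset or reverse the bias. The non-inferiority analysis is unaffected. The change is worth making because it settles, before results are known, which set governs, and it needs no new analysis.

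**What to change.** Add to section 4.4:

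> Superiority of either treatment will be assessed from the two-sided 95% confidence interval on the FAS by allocated arm, using sensitivity analysis 2(c), with 2(a) and 2(b) as checks on missing endpoints. The PP result is supportive; if the two sets disagree on superiority, the FAS governs.

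The PP stays primary for non-inferiority. Superiority should not be made conditional on non-inferiority, because superiority of anticoagulants could then be blocked. Enumerating all event pairs at an assumed 95 per arm, every interval for antiplatelet minus anticoagulant that lies above zero has an upper limit of at least 13.8 points (6 vs 0 events), beyond the 12-point margin. That minimum depends on arm size: it is 11.0 points at 120 per arm and 6.7 at 200.

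The cost is one or two sentences, plus some power for superiority when cross-over is common. Assume true rates of 8% vs 25%, 95 per arm, exclusion unrelated to outcome, and switchers taking the other arm's full risk (a pessimistic case). With 5% vs 5% cross-over (lower-risk arm first), power is 85% on the PP and 78% on the FAS. With 5% vs 15% it is 83% and 69%.

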4.5 Supportive analyses and sensitivity analyses

The following supportive and sensitivity analyses will be conducted to support the main analysis described above (Section 4.3). The rationale for each sensitivity analysis is indicated in bold. All sensitivity analyses except for the sensitivity analysis nr 2 will be performed on the PP. Missing values will be handled as described in section 5.2 if not defined otherwise.

1. **Missing values:** In case of missing values for the primary endpoint, the main analysis will be repeated performing the following imputations

³In the protocol, this was planned as sensitivity analysis. However, given the rather young patient population, we do not expect preexisting micro- or macrobleeds. Therefore the probability of falsely labeling an existing microbleed as new due to missing baseline T2* - or SWI MRI was considered to be small and the aim to preserve the randomization was of overriding importance. Therefore the two analyses were switched.

- (a) Missing values in the primary endpoint will be imputed as CIHD events (assuming the worst for patients without follow-up).
 - (b) Missing values in the primary endpoint will be imputed as no CIHD events (assuming the best for patients without follow-up).
2. **Choice of analysis population (PP vs. FAS):** The analysis will be repeated on the FAS and compared to the main analysis. According to the intention-to-treat principle, each patient will be analyzed according to the treatment she/he was randomly allocated to. In case of missing values for the primary endpoint, the following imputations will be performed:
 - (a) Missing values in the primary endpoint will be imputed as CIHD events (assuming the worst for patients without follow-up).
 - (b) Missing values in the primary endpoint will be imputed as no CIHD events (assuming the best for patients without follow-up).
 - (c) Patients with missing values in the primary endpoint will be excluded from the analysis. Inverse probability of censoring weights will be used as described for the main analysis in section 5.2.
3. **Incomplete information about micro- or macrobleeds at baseline:** The main analysis will be repeated excluding patients without baseline information with regards to micro- or macrobleeds.
4. **Effect of failure to preserve the randomization due to major protocol deviations:**⁴ We will use stabilized inverse probability weights to assess the impact of patients excluded from the PP analysis set according to (Robins et al., 2000) and (Hernan & Robins, 2006; Austin & Stuart, 2015). The weights will be estimated on the FAS. Thereby we will use the following variables: age, sex, occlusion of dissected artery and National Institutes of Health Stroke Scale (NIHSS). If the patient did not have a stroke, 0 will be imputed for the NIHSS. Thereafter the main analysis will be repeated including the weights. By doing so, patients without deviation who are similar to the patients with deviation will be inflated (compared to and patients without similarities).
5. **Assessing a modelling approach:** we compare the probability of CIHD between trial arms using a logistic regression model. The incidence of CHID will be the dependent variable. Treatment will be used as independent factor. In addition, the model will include the presence of cerebral ischemic events clinically and/or neuroradiologically (i.e., clinically defined ischemic stroke, or DWI-lesions at baseline, or both) and occlusion of the dissected artery as covariates to adjust for baseline differences among patients.
6. **Effect of minor protocol deviation:**⁵ The main analysis will be repeated excluding patients who were randomized or initiated treatment more than 72h after initial MRI scan, which was considered to be a minor protocol deviation.

⁴This sensitivity analysis was not planned in the protocol. However we think it helps to further assess the potential bias introduced when randomized patients are excluded from the analysis set due to major protocol deviations.

⁵This sensitivity analysis is a consequence of the adaption in section 2 ("major" vs. "minor" protocol deviations).

7. **Effect of imaging endpoint (as compared to clinical endpoints):**⁶ The main analysis will be repeated including only the clinical endpoints ICH, stroke, extracranial hemorrhage and death as components of the primary endpoint.

All patients with a primary or secondary outcome event will be listed by the PI. For the primary outcome events, the PI will provide information on type, timepoint of the outcome event and relation to the allocated treatment (antiplatelets vs anticoagulants). Laboratory values quantifying coagulation at the time of the event will be provided if available.

5 Secondary objective

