5.2 Missing values

Primary endpoint In patients with missing information on micro- or macrobleeds at baseline, any lesion detected on follow-up T2*- or SWI MRI will be considered as new lesion (section 4.1 and sensitivity analysis 3). For missing values in the primary endpoint (e.g. due to missing follow-up), inverse probability of censoring weights will be estimated. Thereby stabilized inverse probability of weights for missingness of the primary endpoint will be estimated for each treatment arm according to (Robins et al., 2000) and (Hernan & Robins, 2006; Austin & Stuart, 2015). The weights will be estimated on the PP except for the sensitivity analysis 2, where the FAS will be used. The following variables will be used to estimate the weights: age, sex, occlusion of dissected artery, and National Institutes of Health Stroke Scale (NIHSS). If the patient did not have a stroke, 0 will be imputed for the NIHSS. Missing values will be further investigated in sensitivity analyses (see sensitivity analysis 1).

Covariates Missing values in covariates used to estimate the inverse probability of censoring weights will be imputed. If the number of missing values does not exceed 5% in each variable of interest the median (continuous variables) or the mode (= most frequent category, categorical variables) will be used. If there is one covariate with more than 5% missing values, 5 multiple imputations will be done as described in van Buuren & Groothuis-Oudshoorn (2011). To this end we will generate 5 imputed data sets. In a second step we will estimate the weights for each imputed data set. Thereafter, we will stabilize and average the weights over the 5 imputations. In case of severe variability of the stabilized weights between imputations, we will increase number of imputations. Thereby the weights will be considered to have "severe variability between imputations" if for any patient the inter-weight variability divided by the number of imputations (the amount the variance would be increased in order to correct for the uncertainty of the imputations when using Rubin's rule, Barnard & Rubin (1999)) is larger than 0.01.

Secondary endpoints: The number of missing values will be presented. No imputations will be performed. Secondary analyses will be complete case analyses.

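### Sensitivity analysis 4 should fit its weights within each randomized arm; as written, they leave bias from arm-dependent exclusions essentially unchanged

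*SAP*

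**What the plan says.** The PP is the primary analysis set (SAP section 4.3). Section 2 lists the deviations that remove a patient from it. Some concern entry, such as "no dissection: diagnostic criteria for CAD not met in central MR reading". Others arise after randomization: "switching between treatment groups (cross-over) or discontinuation of the allocated treatment before follow-up visit 2 for any reason other than" a reaction to a primary outcome event or an SAE; "MRI at follow-up visit 1 earlier or later than 14 +/- 10 days"; and a second follow-up visit before day 60. Section 1 describes the trial as open label with blinded outcome assessment.

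Item 4 of section 4.5 applies stabilized inverse probability weights to the PP. Its footnote gives the aim, which is to assess the "potential bias introduced when randomized patients are excluded from the analysis set due to major protocol deviations". The model is specified as "The weights will be estimated on the FAS. Thereby we will use the following variables: age, sex, occlusion of dissected artery and National Institutes of" (the list ends with the NIHSS), with zero entered for patients without stroke. Arm is not in the list, and nothing says that the model is fitted by arm.

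Section 5.2 uses the same four covariates and the same references for missing outcomes, but there "stabilized inverse probability of weights for missingness of the primary endpoint will be estimated for each treatment arm". The introduction to section 4.5 points to section 5.2 for missing values only, so it does not carry by-arm fitting over to the exclusion weights.

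**The concern.** Excluding patients disturbs the comparison between arms when different kinds of patients are lost from each arm. In an open-label trial that is plausible for cross-over and discontinuation, and possible for MRI or visit timing. A weight that depends on covariates alone is the same for like patients in both arms, so it cannot rebalance arms that have lost different kinds of patients.

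At stake is what item 4 can show. If its result matches the main analysis, the natural reading is that PP exclusions did little harm. With pooled weights, the two results would match closely whether or not arm-dependent selection on these covariates had occurred.

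**Working it through.** **Inputs.** From the SAP: the margin of 0.12 (section 4.2), the item 4 covariate list, and by-arm fitting in section 5.2. The SAP gives no event or exclusion rates, so all rates below are assumptions, and there is no figure of the plan's own to reproduce.

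**Set-up.** Take 1:1 arms and one binary prognostic marker standing for the covariates, with prevalence p. CIHD risk is r1 with the marker and r0 without it, the same in both arms, so the true difference is 0. The exclusion probability in arm a is e(a,1) with the marker and e(a,0) without. Under weights w, the marker share in the PP of arm a is

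s(a) = p(1−e(a,1))w(a,1) / [p(1−e(a,1))w(a,1) + (1−p)(1−e(a,0))w(a,0)].

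The estimated difference, antiplatelet minus anticoagulant, is (r1−r0) × [s(antiplatelet) − s(anticoagulant)]. The stabilizing constant cancels within each arm.

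**One case in full.** p = 40%, r1 = 30%, r0 = 15%. Exclusions with/without the marker are 30%/5% on antiplatelet and 5%/20% on anticoagulant.

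- Unweighted: s(antiplatelet) = 0.28/(0.28+0.57) = 0.3294; s(anticoagulant) = 0.38/(0.38+0.48) = 0.4419. Difference = 0.15 × (0.3294−0.4419) = −1.69 points.
- Pooled weights: retention with the marker is (0.70+0.95)/2 = 0.825, and without it (0.95+0.80)/2 = 0.875. Then s(antiplatelet) = 0.3394/(0.3394+0.6514) = 0.3425 and s(anticoagulant) = 0.4606/(0.4606+0.5486) = 0.4564. Difference = 0.15 × (0.3425−0.4564) = −1.71 points.
- By-arm weights: both shares return to 0.40. Difference = 0.00.

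**Range of assumptions** (true difference 0; exclusions with/without the marker; results in percentage points).

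| p | r1 / r0 | Excl. antiplatelet | Excl. anticoagulant | Unweighted | Pooled | By arm |
|---|---|---|---|---|---|---|
| 40% | 30% / 15% | 30% / 5% | 5% / 20% | −1.69 | −1.71 | 0.00 |
| 40% | 45% / 10% | 30% / 5% | 5% / 20% | −3.94 | −3.99 | 0.00 |
| 40% | 30% / 15% | 20% / 10% | 10% / 15% | −0.63 | −0.63 | 0.00 |
| 35% | 35% / 10% | 35% / 5% | 10% / 10% | −2.02 | −2.15 | 0.00 |
| 35% | 35% / 10% | 35% / 5% | 5% / 25% | −3.41 | −3.47 | 0.00 |
| 35% | 35% / 10% | 20% / 8% | 10% / 10% | −0.78 | −0.79 | 0.00 |
| 35% | 35% / 10% | 32% / 12.5% | 15% / 5% | −0.75 | −0.80 | 0.00 |

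When exclusion depends only on the marker, or only on arm, all methods give 0.00. Swapping the arms' exclusion patterns reverses the signs.

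**With a true difference.** Take p = 35%, risks of 38%/16% on antiplatelet and 30%/8% on anticoagulant (true difference +8 points), and the exclusions of the fourth row. The unweighted PP gives 6.22, pooled weights 6.11 and by-arm weights 8.00.

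**Arm as a main effect only.** Adding arm to the logistic weight model without interactions gives −1.70, −3.52, −0.72 and +0.01 in the last four rows. It works only in the last row, where arm and marker effects are additive on the logit scale.

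**What pooled weights do achieve.** Take p = 40%, anticoagulant risks of 30%/15% and a relative risk of 1.5 on antiplatelet, so 45%/22.5%. The FAS difference is (0.4×45 + 0.6×22.5) − (0.4×30 + 0.6×15) = 31.5 − 21.0 = 10.5 points. With 30%/5% exclusion in both arms, the marker share in the PP is 0.3294. The unweighted difference is 29.9 − 19.9 = 10.0, and pooled weights restore 10.5.

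**The case against.** **Arm may be unlisted because by-arm fitting was intended.** Section 5.2 does not list arm among its variables either, since its model is fitted by arm, and item 4 shares its covariates and references. So a reader should not infer that the authors chose a pooled model. The intention cannot be known from the text, but the instruction as it stands leads to a single model on the FAS, and by-arm fitting is stated in one place and not in the other.

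**Item 4 does not stand alone.** A reader might infer that it is the only safeguard against bias from removing switchers and stoppers. The SAP does not support that. Item 2 repeats the analysis on the FAS as randomized, which keeps those patients in, and its variant (c) uses the section 5.2 weights. The footnote to item 4 presents it as a further assessment. Item 5 adjusts for occlusion and baseline ischemia in the PP, which covers part of the covariate list but not age, sex or NIHSS. These points stand and limit the consequence. Item 4 is still the only analysis that reweights the PP for its exclusions.

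**Pooled weights are not useless.** Where the treatment effect varies with a covariate, they restore the FAS mix, as the last calculation shows.

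**The larger biases rest on steep assumptions.** Figures near 4 points need opposite exclusion patterns and a strong risk contrast. Section 2 also keeps in the PP patients who switch or stop in reaction to a primary outcome event or an SAE, which weakens one route to arm-dependent selection.

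**Patients without a dissection.** A reader might infer that they should be taken out of the weight model. Item 4 targets all patients excluded from the PP, so including them follows its stated aim. Removing them would change the target population and is not needed for the by-arm correction.

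**Conclusion.** The point holds for item 4 as written. Pooled weights leave bias from exclusions that depend jointly on arm and prognosis essentially where it was: within 0.13 points of the unweighted PP result in every case above. Under the assumed rates the remaining bias is about 0.6 to 4 points against the 12-point margin. None of those rates comes from the SAP, and the bias is nil where exclusion does not depend on arm and prognosis together. The issue is not confined to switching and stopping, because MRI-window and early-visit exclusions also occur after randomization.

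The primary estimate does not change, and item 2 gives another view of PP exclusions. It would go too far to say that the non-inferiority conclusion is compromised. The supported conclusion is that agreement between item 4 and the main analysis would be weaker evidence of robustness than it appears.

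**What to change.** State in item 4 that the stabilized weights for remaining in the PP are estimated on the FAS separately in each randomized arm, with the same four covariates, as in section 5.2. A single model with all arm-by-covariate interactions would serve equally; arm as a main effect alone would not. If by-arm fitting was already intended, the sentence simply records it.

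The cost is one sentence and the same code run by arm, with slightly more variable weights because each model uses one arm only. The report should add that the weights correct only for the four baseline covariates, not for unmeasured or post-baseline reasons for exclusion.
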